## Study Goals and Objectives

### *Aim 1: Reduce or Contain Prescription Opioid Use While Maintaining Pain Control.*

Hypothesis 1a. At one year, 40% of participants in the Taper Only group (no behavioral treatment) will successfully reduce prescription opioids by  $\geq 50\%$  in MEDD without worsening pain intensity, pain interference, or satisfaction with social roles and activities at 12 months.

Hypothesis 1b. Success with patient-centered opioid tapering will not be associated with the starting MEDD.

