#### **Sample Size Calculations and Study Power**

The power calculation is primarily based on the study aims for comparative effectiveness. The original power calculation was for  $N = 850$ , with  $N = 750$  patients completing the month-12 survey. The study sample size was later reduced to  $N = 489$  participants completing the month-12 survey ( $n = 163$  patients per intervention arm on average). As a result, the study's power is lower than initially planned but remains adequate for the objectives, summarized as follows:

*Hypothesis 1a.*  $N = 163$  Taper Only participants provide 80% power to confirm that the taper success rate is above 40% at a two-sided significance level of 0.05, when the true success rate is 51.5%.

*Hypothesis 1b.* Comparing the taper success rate between  $n = 140$  Taper Only participants with an initial dose  $< 200$  MEDD and  $n = 23$  Taper Only participants with an initial dose  $\geq 200$  MEDD, the expected 95% confidence interval (CI) for the difference in success rates is [-22%, 22%], assuming a true taper success rate of 50% independent of the initial dose. The width of the CI increases by only 24% due to the sample size reduction.

*Hypothesis 2a.*  $N = 163$  participants per intervention arm provide 80% power for detecting a taper success rate difference of 40% versus 53.5% at a two-sided significance level of 0.05.

*Hypothesis 2b.*  $N = 163$  participants per intervention arm yield an expected 95% CI of [-11%, 11%] for estimating the difference in taper success rates between the Taper + pain-CBT and Taper + CPSMP arms, assuming a taper success rate of 50% in both arms.

*Hypothesis 2c and 2d.*  $N = 163$  participants per intervention arm provide 80% power to detect a between-group difference of 0.311 standard deviation in the 12-month change of continuous outcomes using a two-sample t-test at a two-sided significance level of 0.05.

We also assume an annual drop off rate is less than 19% and we will include all drop outs in our ITT analyses. We will enroll a total of 594 patients to assure the minimum group size requirements for analysis of comparative effectiveness.

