#### **Statistical Analysis Plan**

*Aim 1:* Reduce or contain prescription opioid use while maintaining pain control.

*Hypothesis 1a:* We will estimate the proportion of patients achieving patient-centered opioid taper success and test whether this proportion exceeds 40% (treatment success estimate derived from Darnall et al.). We will estimate the binomial proportion of patients with opioid taper success and use the exact test to test whether the proportion is greater than 40%.

*Hypothesis 1b:* We will compare opioid tapering success rates among patients in different initial opioid dose categories: Low (10–49 MEDD), Moderate (50–89 MEDD), High (90–199 MEDD) and Super-High ( $\geq 200$  MEDD).

**Aim 2:** Examine the balance in key patient characteristics such as initial opioid dose, pain intensity, and functional measures separately for the three interventions arms. We will use Chi-square or Fisher's exact tests to compare success rates between opioid dose groups.

***Hypothesis 2a:*** We will compare the intervention success rate of 500 patients in behavioral intervention arms (pain-CBT and CPSMP) with 250 patients receiving patient-centered opioid tapering only (no behavioral intervention; Taper Only). We will use a Chi-square test to compare the success rate between groups. We will apply logistic regression to adjust for baseline covariates.

***Hypothesis 2b:*** We will estimate the difference in intervention success rates between pain-CBT and CPSMP arms using an intention-to-treat procedure and construct 95% CIs for the difference.

***Hypothesis 2c:*** We will compare changes in pain intensity, pain interference, and depression scores (baseline to 12 months) between the pain-CBT and Taper Only as well as between the pain-CBT and CPSMP arms using two-sample t-tests. We will apply an analysis of covariance based on multiple regression to adjust for baseline covariates.

***Hypothesis 2d.*** We will compare improvements in satisfaction with social roles and activities, and self-efficacy for Taper + CPSMP against Taper + pain-CBT and Taper Only.

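### Hypothesis 1b claims no association with starting dose, but the SAP names only a difference test for it and leaves out the confidence interval on which 1b was planned

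*Combined protocol and SAP*

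**What the plan says.** Under Aim 1 of the Study Goals and Objectives, Hypothesis 1b reads: "Success with patient-centered opioid tapering will not be associated with the starting MEDD".

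In the Statistical Analysis Plan, the paragraph for 1b says "We will compare opioid tapering success rates among patients in different initial opioid dose categories" and lists them as "Low (10–49 MEDD), Moderate (50–89 MEDD), High (90–199 MEDD) and Super-High" (200 MEDD or more). The only method that fits this comparison is a sentence printed a few lines lower, under Aim 2: "We will use Chi-square or Fisher's exact tests to compare success rates between opioid dose groups". Its reference to dose groups matches 1b and none of the Aim 2 hypotheses. No interval, margin or decision rule accompanies it.

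The Sample Size Calculations section treats 1b as an estimate of one contrast in the Taper Only arm: 140 participants starting below 200 MEDD against 23 starting at or above it. It gives the expected 95% CI "for the difference in success rates is [-22%, 22%], assuming a true taper success rate of 50% independent of the initial dose". Neither that contrast nor that interval reappears in the SAP under 1b.

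Hypothesis 2b, the other hypothesis of no difference, is handled by interval: the SAP specifies a 95% CI for pain-CBT against CPSMP and later says it will be used to judge equivalence.

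**The concern.** A Chi-square or Fisher test can produce evidence against 1b but not evidence for it. If it is the only analysis named, the sole outcome that looks favourable to 1b is a p-value above 0.05. That outcome is also what a small subgroup tends to produce whether or not an association exists.

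1b is one of the two hypotheses under Aim 1. A report that success did not depend on starting dose would be read as applying to patients at 200 MEDD or more, of whom the plan expects about 23 in the Taper Only arm. The question is how often the named test would stay silent when those patients, or patients along the whole dose range, do worse.

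**Working it through.** **Inputs from the documents.** 140 and 23 Taper Only participants below and at or above 200 MEDD; 50% success regardless of dose; four dose categories, hence 3 degrees of freedom; 95% CI.

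**Assumptions.** Two-sided 0.05 for the test (no level is stated for 1b). The sizes of the three lower categories are not given, so three splits of the 140 were tried: 47/47/46, 80/35/25 and 30/40/70. The deficits below are also assumed; the documents give none.

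**The plan's own figure.** Half-width = 1.96 × √(0.25/140 + 0.25/23) = 1.96 × 0.1125 = 0.2205, or 22 points. The ratio of widths before and after the sample size reduction is √(250/163) = 1.238, the stated 24% increase. Both reproduce.

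**Four-group Chi-square, 15-point deficit at 200 MEDD or more.**
- Overall rate: (140 × 0.50 + 23 × 0.35)/163 = 78.05/163 = 0.4788.
- Noncentrality: Σ nᵢ(pᵢ − p̄)² / [p̄(1 − p̄)] = [140 × 0.0212² + 23 × 0.1288²]/(0.4788 × 0.5212) = 1.78.
- Power on 3 df: 17.5%; about 17% by simulation. The test misses the deficit about 83% of the time.

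The split of the 140 does not enter this formula when the lower three categories share one rate, and simulated power hardly moved across splits.

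**Other patterns, same test.**

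| Assumed truth | Power | Missed |
|---|---|---|
| Top group 10 points lower | about 10% | about 90% |
| Top group 15 points lower | about 17% | about 83% |
| Top group 20 points lower | 28–29% | 71–72% |
| Top group 25 points lower | about 44% | about 56% |
| Top group 30 points lower | 60–63% | 37–40% |
| Steady decline 62.5/54/46/37.5% | 36–48% by split | 52–64% |

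**Two-group comparison, 140 v 23.** For a 15-point deficit in the top group, Chi-square power is about 26% and Fisher power about 24%, so it misses 74–76%. For the steady decline, two-group Chi-square power is 32%, 43% and 24% across the three splits, against 42–43%, 48% and 36% for the four-group test. Which comparison is more sensitive therefore depends on the pattern.

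**If all arms were pooled.** The SAP says patients without naming an arm. With 489 in the same proportions (420 and 69), the four-group test still misses a 15-point deficit about 53% of the time.

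**What the planned interval could show.** With no true difference and standard error 0.1125, the chance that the whole 95% CI lies inside ±m is 2Φ(m/0.1125 − 1.96) − 1, floored at zero. This gives 0% for m = 15 or 20 points, 21% for 25 and 52% for 30.

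**The case against.** Protocol and SAP form one document, and the sample size section frames 1b entirely as an interval, with no power or significance level. The SAP also has a post-hoc logistic regression of baseline characteristics on success. It would therefore be wrong to say that 1b is judged by a significance test alone. This stands. The narrower fault is that the SAP names only the test for 1b and does not bring the interval forward; the post-hoc regression is not tied to 1b.

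A reader might infer that the plan will declare 1b confirmed when p > 0.05. No passage says so: the SAP says only that rates will be compared. The supported statement is that no rule is given and that, with the test alone, nothing else could count in favour of 1b.

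A reader might also infer that the four-group test is simply the weaker choice because it spends 3 degrees of freedom. That holds only when the whole effect sits at 200 MEDD or more. For the graded decline it is the more sensitive of the two. It follows that the below-200 against 200-or-more contrast should not become the only 1b result: the hypothesis concerns starting MEDD in general, and the contrast averages away differences below 200.

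Finally, the limiting factor is 23 patients, which no analysis removes and which the ±22 points already discloses. This is true, and it is the reason to present 1b as estimation.

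**Conclusion.** The concern holds as a mismatch between a no-association hypothesis and the method named for it, together with the loss of the planned interval between the sample size section and the SAP. In the Taper Only arm, a non-significant four-group test would be the likely result for a top-group deficit of 15 points (missed about 83%) or 25 points (about 56%), and for a steady 62.5%-to-37.5% decline (52–64%). At 30 points the test would more often detect the deficit than miss it.

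These sizes rest on 140 and 23 participants, 50% success elsewhere, two-sided 0.05 and deficits chosen for illustration. The planned interval does not rescue a claim of no association: at ±22 points it cannot fit inside a margin of about 20 points or less, even with an observed difference of zero.

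The 13.5-point difference in the sample size section (40% v 53.5%) might be taken as a ready-made margin. The documents present it as the difference detectable for Hypothesis 2a and never call it a threshold of relevance, so the conclusion does not lean on it.

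The SAP should be changed, because the change alters what may be concluded from 1b and needs no new data.

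**What to change.** In the SAP under Hypothesis 1b:
- Give taper success rates with 95% CIs in all four dose categories.
- Give the difference in success between participants below 200 MEDD and those at or above it, with its 95% CI, as planned in the sample size section.
- Report alongside it, with equal standing, a logistic regression of success on log baseline MEDD (odds ratio with 95% CI), so that gradients below 200 MEDD remain visible.
- Keep the Chi-square or Fisher p-value as supplementary, and move its sentence from Aim 2 to 1b.
- State that p > 0.05 will not be reported as absence of association, and that the conclusion is the range of differences the CIs exclude.
- Name the arm or arms in which 1b is analysed.

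In the Sample Size section, add that the expected ±22 points makes 1b an estimation objective that cannot establish absence of association within margins of about 20 points or less.

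The cost is wording and one regression on data already collected, with no extra patients. The downside is that 1b can no longer draw support from a non-significant test, so its conclusion will be weaker.

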### *Aim 2: Compare the Effectiveness of (1) Taper + CPSMP, or (2) Taper + pain-CBT, or (3) No Behavioral Treatment (Taper Only) within the Context of Patient-Centered Collaborative Opioid Tapering.*

Hypothesis 2a. Participants receiving behavioral interventions (Taper + pain-CBT or Taper + CPSMP) will be more likely to reduce their opioid dose than those in the Taper Only group (no behavioral intervention).

Hypothesis 2b. There will be no significant differences in dosage reduction or the percentage of participants reducing dosage between the Taper + pain-CBT and Taper + CPSMP groups.

Hypothesis 2c. Participants in the Taper + pain-CBT group will experience less pain, less pain interference, and decreased depression compared to those in the Taper + CPSMP or Taper Only groups.

Hypothesis 2d. Participants in the Taper + CPSMP group will show greater improvements in satisfaction with social roles and activities and self-efficacy compared to those in the Taper + pain-CBT or Taper Only groups.

*Exploratory Hypothesis 2e.* Opioid escalation will be less common among participants in the behavioral intervention groups (Taper + pain-CBT or Taper + CPSMP) compared to those in the Taper Only group.

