## Study Design

This is a pragmatic, prospective, longitudinal, multi-center, three-arm, randomized controlled clinical trial. The study will include 594 patients receiving daily prescription opioids in primary care and pain clinics at EMPOWER study sites (see Table 1 for a list of study locations).

[figure not shown]

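### The SAP sizes Hypothesis 2a at 500 v 250 patients, which a trial of 594 cannot supply, and sets no primary rule for a dropout's month-12 taper success

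*Combined protocol and SAP*

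**What the plan says.** **Sizes.** Study Design: "The study will include 594 patients receiving daily prescription opioids". Sample Size Calculations and Study Power repeats this: "We will enroll a total of 594 patients to assure the minimum group size requirements". That section also explains that an earlier plan of 850 enrolled and 750 completing month 12 was cut to 489 completers, 163 per arm on average. Statistical Analysis Plan, Hypothesis 2a, nevertheless reads: "We will compare the intervention success rate of 500 patients in behavioral intervention arms", set against 250 Taper Only patients.

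**Contrast and power.** Aim 2, Hypothesis 2a, takes the two behavioral arms together and predicts that they "will be more likely to reduce their opioid dose than those in the Taper Only group". The power statement is that 163 "participants per intervention arm provide 80% power for detecting a taper success rate difference of 40% versus 53.5" percent, two-sided 0.05.

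**Test.** Under Hypothesis 2a: "We will use a Chi-square test to compare the success rate between groups". The summary later in the same SAP names Fisher's exact test for this comparison and words it by the intervention participants received. Access and Intervention Participation makes intention-to-treat (ITT) the basis for comparisons across interventions and treats as-received comparisons as a sensitivity analysis.

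**Dropouts.** The sample size section assumes annual dropout below 19% and adds "we will include all drop outs in our ITT analyses". The Sensitivity Analysis paragraph promises analyses for missing data without naming a method. For Hypothesis 1a the plan will "use the exact test to test whether the proportion is greater than 40" percent.

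**The concern.** The 500 and 250 stand in the operative SAP, not in a change log. An analyst or reader who takes them at face value has the wrong denominators and an inflated idea of power for the main between-arm comparison. The same comparison also carries two test names and two descriptions of who is compared.

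The second matter has more substance. Taper success needs both opioid dose and pain intensity at month 12. About 105 enrolled patients are expected to lack the month-12 survey, yet they are to enter the ITT analyses. Without a primary rule, the success rates and their difference depend on a choice that the plan leaves open. The mixed model in the SAP does not fill the gap, because it covers only the continuous secondary outcomes.

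**Working it through.** **Inputs.** From Sample Size Calculations and Study Power: 594 enrolled; 489 completers; 163 per arm; 53.5% v 40%; two-sided 0.05; and, for H1a, 51.5% against 40%. From the SAP: 500 v 250. Assumed here: equal arms (594/3 = 198 enrolled and 163 completers per arm) and equal dropout across arms.

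**1. Can 500 v 250 occur?** 500 + 250 = 750, more than the 594 enrolled. It equals the superseded number of completers. The current sizes are 2 × 163 = 326 v 163 with month-12 data, or 2 × 198 = 396 v 198 enrolled.

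**2. Reproduce the stated 80% for H2a.** Power = Φ[(d − 1.96·SE0)/SE1], where SE0 = √{p̄(1−p̄)(1/n1 + 1/n2)} and SE1 = √{p1(1−p1)/n1 + p2(1−p2)/n2}.
- 326 v 163: p̄ = (326 × 0.535 + 163 × 0.40)/489 = 0.490; SE0 = 0.0480; SE1 = 0.0473; (0.135 − 1.96 × 0.0480)/0.0473 ≈ 0.867; power **80.7%**. The stated figure reproduces.
- 500 v 250: SE0 = 0.0387; SE1 = 0.0382; z ≈ 1.548; power **93.9%**.
- 163 v 163, one arm against one arm: **68.7%**. This does not reproduce the stated figure, so the plan's 80% refers to the pooled contrast.

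**3. Does the choice of test matter?** Full enumeration at 326 v 163 gives 81.0% for chi-square (no continuity correction) and 79.2% for Fisher's exact test. The difference is small.

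**4. Dropouts in H2a.** 594 − 489 = 105, or 17.7%, about 35 per arm. This agrees with the assumption of less than 19%.

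| Treatment of dropouts (assumed) | Rates compared | n | H2a power |
|---|---|---|---|
| Completers only | 53.5% v 40.0% | 326 v 163 | 80.7% |
| Multiple imputation by arm, missing at random, no auxiliary data (simulated) | 53.5% v 40.0% | 396 v 198 | about 81% |
| Every dropout counted as a failure | 44.0% v 32.9% | 396 v 198 | 74.5% |
| Dropout outcomes all observed, at the completer rate | 53.5% v 40.0% | 396 v 198 | 87.7% |

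The failure rates are 0.535 × 163/198 = 0.440 and 0.40 × 163/198 = 0.329, so the difference falls from 13.5 to 11.1 points. At 19% dropout the corresponding power is 73.3%. The last row needs real outcomes on everyone; imputed values do not add that information.

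**5. H1a, exact binomial, upper tail 0.025.** On 163 against 40%, the test rejects at 79 or more successes and power at 51.5% is 80.3%, which reproduces the plan. If the set were 198:
- outcomes observed on all, at 51.5%: 88.6% (again this assumes that dropout outcomes are observed);
- dropouts as failures, true rate 0.515 × 163/198 = 42.4%, null still 40%: 8.5%;
- the same, with the null on the same basis, 0.40 × 163/198 = 32.9%: 78.3%.

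**The case against.** The strongest reply is that the sample size section openly records the reduction from 750 to 489 completers, so 500/250 is leftover text that alters no contrast or decision, and the stated 80% is right. Most of this stands. The error is editorial in origin, but it remains in the current analysis text and should be corrected.

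It can also be said that sizing on completers with inflated enrollment is about right under missing-at-random. That stands too: imputation by arm gives much the same power as the completer calculation. It does not supply the missing rule.

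There is real mitigation. Dose data come from the medical record as well as surveys, an extra $50 is offered to month-12 non-responders, patients who increase their dose stay in follow-up, and the data analytic team is masked through data collection. These should reduce missing data and the scope for a results-driven choice. But no section says how a record dose is used when the survey is missing, and pain intensity is self-reported.

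A reader might go further and infer that H2a has only 68.7% power. The documents do not support that, because both Aim 2 and the SAP define H2a as the pooled behavioral arms against Taper Only. A reader might also infer that H1a is left with 8.5% power. That needs H1a to be an ITT analysis, dropouts scored as failures, and an unchanged null. The ITT statement in Access and Intervention Participation concerns comparisons across interventions, the SAP attaches ITT by name only to H2b, and the one-arm H1a test is sized at 163 and nowhere called ITT in the text available.

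**Conclusion.** The 500 v 250 in the SAP is wrong as written. It overstates the H2a sizes by about half (750 against 489 with month-12 data) and implies 93.9% power where the plan has 80.7%. The stated 80% itself is correct for the pooled contrast and lacks only a label. The two test names, and the wording by intervention received, are minor inconsistencies.

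The absence of a primary rule for dropouts' taper success in H2a and H2b is a genuine gap of moderate size. Under equal arms and equal dropout, H2a power runs from about 74.5% (failures) to near 80% (imputation under missing-at-random). It does not show that the trial is underpowered, and the 87.7% and 88.6% figures should not be taken as a gain from ITT.

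For H1a the supportable statement is that its analysis set, and whether the 40% null taken from the cited pilot is a completer or an all-enrolled rate, are unclear. The gap between 8.5% and 78.3% shows why both need stating; neither is a forecast for this trial. A few parts of the document were not available, so the finding about missing rules is limited to the text that was.

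**What to change.** 1. In SAP Hypothesis 2a, replace 500 and 250 with about 396 v 198 randomized, of whom 326 v 163 are expected to have month-12 data, noting the equal-arm assumption.
2. In the sample size section, label the H2a power as pooled behavioral arms v Taper Only.
3. Name one test for H2a, on arms as randomized, and keep as-received comparisons as a sensitivity analysis.
4. Pre-specify the primary handling of missing month-12 taper success for H2a and H2b: multiple imputation by arm of month-12 dose (MEDD) and pain intensity from the repeated surveys and any available record dose, then apply the success definition. Name dropout-as-failure and completer-only as sensitivity analyses, and restate power on the chosen basis. Any power quoted on the full 396 v 198 or 198 should say that it assumes observed outcomes.
5. For H1a, state the analysis set and whether the 40% null is a completer or an all-enrolled rate.

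Items 1 to 3 are wording changes at no cost. Item 5 needs a check of the pilot and a sentence. Item 4 costs some programming and rests on missing-at-random, which the sensitivity analyses must probe. Its inputs may be thin for some dropouts, because survey items are optional, patients may withdraw from the study at any time, and no section says that record doses are collected after withdrawal.
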